Conditioned pharmacotherapeutic effects in Psoriasis. Of direct and immediate relevance to the proposed research are the results of a recently completed study (30) conducted at Stanford University and the University of Rochester. In this study, a conditioning component was added to a regimen of topical corticosteroid therapy for

for the reduced cumulative amount of active drug received by the Partial Reinforcement Group, received medication packets each of which contained 25-50% of the dose of steroid previously received. A physician, unaware of group assignments, conducted clinical evaluations weekly using a modified 9-point Psoriasis Severity Scale (PSS). As in the proposed research, it was hypothesized that “relapse,” defined here as a return to within two units of the initial PSS score, and disease severity would be less in patients treated under a intermittent schedule of pharmacologic reinforcement than in patients treated with the same cumulative amount of drug under a continuous schedule of reinforcement. As shown in Fig. 3, the results conformed precisely to predictions: the incidence of relapse in the Partial Reinforcement Group was significantly less than in Dose Control patients. There were no significant differences between the Partial Reinforcement and the Standard Therapy Groups.

There are a number of questions that need to be addressed to get beyond the inference that these results were due to conditioning. It could be argued, for example, that the reduced amount of drug received by the Partial Reinforcement Group was actually an effective dose of medication for psoriasis. However remote that possibility, we have, in the proposed research, added a second Dose Control Group that is treated with drug under the same conditions as the Partial Reinforcement Group but receives no intervening exposures to the CS. Nonetheless, the conclusion to be drawn from this first ever study of conditioned pharmacotherapeutic effects and the hints provided by the studies described above is that it is possible and feasible to introduce an intermittent schedule of pharmacotherapeutic reinforcement into a drug treatment regimen. And, it may indeed be possible to reduce the amount of drug required to control the symptoms of a disease by capitalizing on conditioned pharmacotherapeutic responses.

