b) Number of Subjects: 121. Sample size and Power Analysis: The proposed study will recruit 37 subjects for each of the ST, PR and DC1 treatment conditions, and 10 subjects for the CD2 group. The study has 93% power to detect a 50% difference in relapse rate between group 2 and group 3 over the 2-week assessment period, even account for 10% dropout rate based on a two-sided $\alpha = 0.05$ using the method of Lakatos, E. (35). We selected a 50% relapse rate difference for the power calculation based on our prior experience. For the primary continuous symptom measure blood pressure, we have 80% power to detect about a medium effect size 0.56 based on a longitudinal study design with 7 assessment points, a conservative estimate of within-subject correlation 0.5, and a two-sided type I $\alpha=0.05$ using the method of Tu et al. (36). Note that although blood pressure is assessed twice daily in Experiment 1, we conservatively set the number of assessments at 7 to improve the robustness of the power estimates. Thus, the proposed sample size not only has sufficient power to detect a clinically meaningful difference in relapse rates, but also to find meaningful change patterns for blood pressure over the treatment course.

c) Sex of subjects: The male to female ratio will follow the distribution of hypertension in the Rochester area community. Pregnant or nursing females will be excluded due to the nature of the intervention (carvedilol is Category C). Females of child bearing potential will be required to use 2 birth control methods during the study in order to participate.

d) Age of Subjects: 18 to 80 years of age. Carvedilol is not intended for use in children.

e) Racial and Ethnic Origin: No restrictions. It will follow the distribution of patients seen in the Rochester area.

f) Vulnerable Subjects: None will be enrolled.

III. METHODS AND PROCEDURES

a) **Study Design.** Randomized, single blind.

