Medication. Hypertensive patients will be treated with distinctively colored, *odored and flavored* gelatine capsules (Capsuline, Inc, Pompano Beach, FL) containing 12.5 mg (generic version, available from the Strong Memorial Hospital Research Pharmacy). The “placebo” will be a capsule containing 12.5 mg of an inert substance with the same characteristics as the active drug capsules. Capsules will be packaged in a blister strip of single application packets by the Investigational Drug Studies program in the Strong Memorial Hospital Research Pharmacy. Preparation of the sequence of medication would be done from coded patient numbers and would depend upon the schedule of reinforcement that was being used. For example, if one were imposing a 25% reinforcement schedule (only one fourth of the packets of capsules containing active drug), a random sequence would be constituted with the proviso that the patient would receive no more than two doses of consecutive placebo capsules. Randomization will be performed by the research pharmacy in blocks of eight. Allocation concealment will be guaranteed, since only the research pharmacist will be aware of group distribution and all other members of the research team will be blinded. He will provide the research nurse with the pre-labeled packages.

Length of study: 8 weeks for those subjects that complete the full set of procedures. For those subjects who relapse early, or whose blood pressure does not remit (10-point decrease for a period of 5 days) prior to the Exp 1 phase, the minimal period in the study is 3 weeks.

Exp 1: Baseline Period: 2 weeks after a screening physical examination that will be performed within one week of admission. ; Experimental Phase: 2 weeks (or less for subjects' whose mild hypertension relapses). Therefore, maximal possible period receiving carvedilol: 4 weeks.

Exp 2: 4 weeks. In this experiment subjects either receive placebo or no treatment. We expect the latter group to relapse after a few days. Those receiving placebo are hypothesized to relapse later, and we are assuming that will relapse before 4 weeks on placebo. However, if we find that there are subjects that after 4 weeks have not relapsed, we plan to continue the administration of the placebo until they relapse (beyond the 4 weeks). Because we believe that this will occur rarely, for practical reasons we will state in the consent form that this period may last “up to 4 weeks”.

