The choice of the β/α blocker for this study was based on:

a) targets receptors of the peripheral nervous system (PNS); it is a non-selective β -adrenergic blocking agent with alpha-1 blocking activity. It is approved for use in hypertension as well as heart failure. Other hypotensive drugs could have been chosen, however, their primary target is not “directly” aimed at the PNS or CNS. We are aware that ACE inhibitors decrease catecholamines, and angiotensin receptor blockers decrease vasopressin, however, for this initial study we chose a drug that is mostly associated to the sympathetic system. We believe that this will provide the best chances of success. Future studies will include alternative drugs.

b) Carvedilol has no adverse effect on glycemic control, and is the preferred β blocking agent for patients that have diabetes (as some of ours may).

c) We have preliminary published data (28) that strongly suggests the effectiveness of our conditioning paradigm in the pharmacotherapy of hypertension using a similar β blocker.

d) can be administered two times a day, leading to an enhanced number of “learned” exposures to the stimulus, and this regimen guarantees that subjects in groups that receive only one active drug

administration out of 4 will take adequate daily amounts of that will prevent them from the undesired rebound side effects of this medication that could occur if they were to have 3 days with no active drug.

Subjects will be started on the lowest recommended starting dose of 25 mg daily in 2 fractionated doses, which is reasonable given their level of hypertension (33,34). Once a reasonable blood pressure drop is achieved, they will be randomized to four experimental groups, as described in the methods section.

Potential participants will be informed that the purpose of the study is to determine if their blood pressure could be brought under control using lower amounts of medication and that, in the course of the study, the amount of medication they receive may be reduced. The medical staff with whom the patient comes in contact will not know if or when this occurs. Measurement of blood pressure during the study will be performed by the patients themselves, who will be instructed in the use of automated BP monitors (HEM-711AC, Omron Healthcare Inc., Bannockburn, IL) which will be provided. Subjects will obtain measurements twice (one after the other) in the AM and twice (one after the other) in the PM always at the same time of day.

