A screening physical examination will be performed within one week of admission into the study and only patients, who are in good health, display no contraindications for the use of beta blockers and disclaim the use of antihypertensive medication for at least 2 wk. before the start of the study will proceed to the initial maintenance or baseline period.

Patients will be excluded from participation if they use illicit drugs, were using anti-hypertensive medications within the previous 2 weeks other than ACE-inhibitors, angiotensin receptor blockers, calcium channel blockers, aldosterone antagonists, or diuretics **Patients will be excluded from participation if they use illicit drugs; they use inhalers regularly to control reactive airway diseases like COPD and asthma;** if pregnant or if sexually active women are not using contraceptives; if they cannot be followed or monitored appropriately; or renal insufficiency are determined, which may require a blood draw at the time of screening physical examination if subject has not had basic blood profile done in the past 12 months.

Experiment 1. Effects of a partial schedule of pharmacotherapeutic reinforcement in maintaining the therapeutic effects of in the treatment of hypertension.

The proposed research will determine if, capitalizing on conditioned pharmacotherapeutic effects, patients suffering from hypertension can be effectively treated with smaller cumulative amounts of a beta blocker, . Some patients in this initial experiment will be treated on a partial rather than a continuous schedule of pharmacologic reinforcement. These patients will be compared to: (a) patients that continue to be treated on a standard regimen of pharmacotherapy at the baseline dose, and (b) patients that receive the same (reduced) total amount of medication under a continuous schedule of reinforcement as that received by experimental patients being treated under a partial schedule of reinforcement, and another Dose Control Group that receives at the same dose and frequency as the Partial Reinforcement Group, but receives no interspersed exposures to the CS.

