Patients in a **Standard Therapy Group** will continue to receive 100% of the dose of medication on the same reinforcement schedule (100%) as they received during the baseline (maintenance) period. (12.5 mg) would be taken 2 times daily for 15 additional days. This is a continuation of their standard pharmacotherapeutic maintenance regimen and constitutes one control group.

The **Partial Reinforcement Group** will be treated under a partial (25%) reinforcement schedule. That is, patients will receive the same dose of drug previously received, but only a quarter of the daily packets will contain active drug (12.5 mg); the remaining capsules will contain only an inert substance. Packets will be arranged to ensure that a patient never receives the “placebo” for more than two consecutive times. The selection of a 25% reinforcement schedule is based on the fact that we are using the minimum recommended starting dose of , and lower doses (particularly this much lower) are likely to have minimal if any pharmacologic effect. Therefore, the total daily dose of 6.25 mg. would not be sufficient to sustain the normotensive levels achieved under continuous reinforcement during the baseline period.

Dose Control Group-1, a control for the cumulative amount of drug received by the Partial Reinforcement Group, will be treated twice daily under a continuous (100%) reinforcement schedule, but each packet will contain only 25% of the active drug received during the baseline period.

To be sure that the reduced amount of drug received by the Partial Reinforcement Group is not sufficient by itself to lower blood pressure, a **Dose Control-2 Group** will receive the same active dose as the Partial Reinforcement Group but will not receive CSs on the intervening doses (6.25 mg once every other day).

Table 1. Experimental Protocol

GROUP	BASELINE PERIOD (15 days)			EXPERIMENTAL PERIOD (15 days)		
	Drug Dose*	Reinforcement Schedule**	Freq.	Daily Drug Dose***	Reinforcement Schedule**	Freq.
Standard Therapy	25	100	2xDay	25	100	2xDay
Partial Reinforcement	25	100	2xDay	6.25	25	2xDay

RSRB: 36447 12 V08.03.2016

Dose Control-1	25	100	2xDay	6.25	100	2xDay
Dose Control-2	25	100	2xDay	6.25	100	every other day

* Daily Dosage in mg of antihypertensive medication

** Percentage of treatment occasions when active drug is received

*** Average Daily Dosage in mg of antihypertensive medication

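### Dose Control-2's written dose, and PR's cap of two consecutive placebos, conflict with the requirement that the dose controls match PR's drug

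*Combined protocol and SAP*

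**What the plan says.** The combined protocol and SAP describes the arms in several places.

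- **DC-2, purpose.** The introduction to Experiment 1 says this arm "receives at the same dose and frequency as the Partial Reinforcement Group, but receives no interspersed exposures to the CS". The psoriasis part of the Background says it is "treated with drug under the same conditions as the Partial Reinforcement Group but receives no intervening exposures to the CS", and that it was added to answer the objection that the reduced drug might itself be effective.
- **DC-2, regimen.** The group descriptions under Experiment 1 say that DC-2 has PR's active dose and then, in the same sentence, give 6.25 mg once every other day. Table 1 lists 6.25 mg for DC-2 with frequency every other day, and its footnote defines that column as an average daily dose.
- **PR.** The group description says that "only a quarter of the daily packets will contain active drug (12.5 mg" each), the rest being inert. It adds: "Packets will be arranged to ensure that a patient never receives the" placebo more than twice in a row. Section III a), Medication, uses a 25% schedule as its example and requires that "a random sequence would be constituted with the proviso that the patient would receive no more than two doses of consecutive placebo capsules".
- **DC-1.** It controls for PR's cumulative drug: twice daily, with every capsule at a quarter of the baseline 12.5 mg.
- **Role.** Section III c) makes PR against DC-1 and DC-2 the principal comparison. Section II b) states: "The study has 93% power to detect a 50% difference in relapse rate between group 2 and group 3". In the listed order that is PR against DC-1. It plans 37 patients in each of those arms but only "10 subjects for the CD2 group" (evidently DC-2), with no power stated for that arm.

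**The concern.** Hypothesis 1 compares schedules at the same reduced amount of drug. The Experiment 1 text itself says that PR against Standard Therapy is not critical for judging conditioning, because those groups receive different amounts. The same reasoning applies to the dose controls if their drug falls short of PR's.

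Two written rules make that possible. The DC-2 text halves the average dose that Table 1 shows. PR's two sequencing rules look incompatible, and nothing says which governs. Either shortfall leaves PR with more drug than a control, which favours the conditioning hypothesis. No analysis in section III c) could separate extra drug from conditioning afterwards.

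**Working it through.** **Inputs.** Active capsule 12.5 mg; twice-daily dosing; DC-1 capsule 0.25 × 12.5 = 3.125 mg. The experimental period is 15 days (30 slots) in the Experiment 1 text and Table 1, but 2 weeks (28 slots) in sections II b), III a) and III c). Both are carried through.

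**1. Table 1's average daily doses**

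- PR: 0.25 × 2 × 12.5 = 6.25 mg. Reproduces.
- DC-1: 2 × 3.125 = 6.25 mg. Reproduces.
- DC-2 by the text: 6.25 / 2 = 3.125 mg. Does not reproduce.
- DC-2 at 12.5 mg every other day: 12.5 / 2 = 6.25 mg. Reproduces.

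**2. Can 25% and a cap of two both hold?** With n active capsules there are n + 1 stretches that can hold placebos (before, between and after), each of at most two. The longest sequence covered is n + 2(n + 1) = 3n + 2.

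- 30 slots: 3n + 2 ≥ 30 gives n ≥ 10, or 33.3%. A 25% schedule means 7 or 8. Exact counting gives no admissible sequence with 7, 8 or 9 active capsules, and 66 with 10.
- 28 slots: 3n + 2 ≥ 28 gives n ≥ 9, or 32.1%. A 25% schedule means 7.

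The two rules are incompatible over either length.

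**3. Total drug by governing rule**

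| | 30 slots | 28 slots |
|---|---|---|
| PR, cap governs (minimum) | 10 × 12.5 = 125 mg | 9 × 12.5 = 112.5 mg |
| PR, 25% governs | 7–8 × 12.5 = 87.5–100 mg | 7 × 12.5 = 87.5 mg |
| DC-1 | 30 × 3.125 = 93.75 mg | 28 × 3.125 = 87.5 mg |
| DC-2 at 12.5 mg | 7–8 × 12.5 = 87.5–100 mg | 7 × 12.5 = 87.5 mg |
| DC-2 at 6.25 mg | 7–8 × 6.25 = 43.75–50 mg | 7 × 6.25 = 43.75 mg |

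- Cap governs, PR against DC-1: 125 / 93.75 = 1.33; 112.5 / 87.5 = 1.29.
- Cap governs, PR against DC-2 at 12.5 mg: 125 / 100 = 1.25 to 125 / 87.5 = 1.43 over 30 slots; 1.29 over 28.
- Cap governs, DC-2 as written: 43.75 / 125 = 35% to 50 / 125 = 40% of PR over 30 slots.
- 25% governs, PR against DC-1: 87.5 / 93.75 = 0.93 to 100 / 93.75 = 1.07 over 30 slots; exactly 1 over 28.

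**4. When the excess appears if the cap governs**

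- First 4 days (8 slots): PR at least 2 × 12.5 = 25 mg; DC-1 8 × 3.125 = 25 mg. No forced excess.
- First 7 days (14 slots): PR at least 4 × 12.5 = 50 mg; DC-1 14 × 3.125 = 43.75 mg.

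**The case against.** **The DC-2 figure is a slip.** Probably so. The rest of its own sentence, the introduction to Experiment 1, the Background and Table 1 all fit 12.5 mg every other day; the parenthesis seems to repeat the average daily figure. But the written dosing instruction remains in conflict with the table, and correcting it does not resolve the cap.

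**The 25% rule is the intended one.** It appears more often: in the Medication example, the drug rationale (one active dose in four), the PR description and Table 1. The cap reads as a sequencing proviso. If 25% governs and DC-2 gets 12.5 mg, the arms match to within rounding. That stands, and it makes the DC-1 imbalance conditional. Yet the cap is stated twice, and a pharmacy following it cannot deliver 25%. The remark under Experiment 2 that Standard Therapy had three times more drug does not settle it: 25 / 8.33 = 3 would fit a one-in-three schedule, but the phrase is ambiguous.

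**The impact is limited.** The cap forces no excess over DC-1 in the first 4 days, and DC-2 is a small arm without stated power. Both points are fair, and DC-1 therefore carries more weight than DC-2.

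**A stronger reading of DC-2.** A reader might infer that DC-2 never gets more than half of PR's drug. Half is the ratio of average daily rates when 25% governs. On whole doses over 15 days, 8 DC-2 doses against 7 PR active capsules is 50 / 87.5 = 57%.

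**Conclusion.** The concern holds as two unresolved contradictions in the dosing text. The text's DC-2 regimen averages about half of PR's nominal dose, against Table 1 and the stated purpose of the arm. PR's 25% schedule cannot be built under a cap of two. If the cap governs, PR gets at least 33% (15 days) or 29% (14 days) more drug than DC-1, and more than DC-2 even at 12.5 mg, so a PR advantage in the principal contrasts could be pharmacological.

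A reader might go further and infer that PR against DC-1 is confounded by drug amount as planned. The document does not support that: it never says that the cap overrides 25%. Nor does it give a dose-response figure from which the effect on relapse could be computed. The amounts assume that every capsule is taken as scheduled.

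**What to change.** 1. Correct the DC-2 text to 12.5 mg once every other day. Table 1 then needs no change for this arm.
2. Relax the cap to three consecutive placebos, in both places where it is stated. With 12-hour spacing the longest interval between active capsules is 48 h, below the rebound concern in the drug rationale ("if they were to have 3 days with no active drug").
3. Fix the period and the number of active capsules:
   - **14 days, 7 active of 28:** exactly 25%. PR, DC-1 and DC-2 each get 87.5 mg, and 120 sequences are admissible.
   - **15 days, 8 active of 30:** 26.7%, with 1,206 admissible sequences. PR gets 100 mg, 6.7% above DC-1's 93.75 mg. Either accept this or make DC-1 capsules of 100 / 30 = 3.33 mg. DC-2 starting on day 1 gets 8 doses, 100 mg.

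The cost is protocol wording, the pharmacy's sequence rule and, for the second option if matched exactly, the DC-1 capsule strength. It has to be done before dispensing.

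If the cap of two is kept, restate PR as about 33% (10 of 30, 125 mg, 8.33 mg/day). Raise DC-1 to 125 / 30 = 4.17 mg per capsule and DC-2 to ten 12.5 mg doses, one every 36 h, and revise the 25% and 6.25 mg/day figures throughout. This costs more, because it changes the reinforcement rate and both control doses.

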It is possible that the therapeutic effects of a partial schedule of pharmacologic reinforcement (and, thus, a reduced amount of active drug) will be indistinguishable from a continuous (standard) regimen of pharmacotherapy. That outcome, however, is not critical for evaluating the role of conditioning in pharmacotherapies simply because these groups would have received different amounts of drug. Specifically, *it is hypothesized that patients treated under a noncontinuous schedule of medication will be less likely to show a recurrence of symptoms ("relapse") than patients treated with that same amount of drug administered under a continuous schedule of reinforcement.*

On the first visit, each potential subject will undergo a brief physical examination to record the medical history, sign an informed consent form, and receive instruction in the use of a blood pressure monitor. A strip of medication packets will be supplied at each clinic visit and will be taken by the subject at home, 2

times a day for the duration of the study.. The subject will return to the study center once a week or within 14 days of the drug dispensing cycle; this will allow flexibility for those with travel or work schedule challenges. The study coordinator will email or call to check on safety of the subject in the interim of a weekly clinic visit. Each drug card contains 15 days of study drug to ensure continual dosing in the event a weekly visit is missed. Packets containing medication will be dispensed by code so the patient and the physician will be blinded as to the nature of the medication. To consider the possibility that conditioning might be influenced by immediate stressful life experiences in these patients, we will examine this relationship using two measures of psychological distress administered at weekly intervals: the Hassles Scale, a frequently-used measure of daily stressors or “hassles” and the Impact of Events Scale (IES) (31).

The protocol for Experiment 1 is shown in Table 1. During a baseline period (of a maximum of 15 days), all patients will be treated BID with 12.5 mg. Those who satisfy the criterion of a 10-point decrease in blood pressure for a period of 5 days will be assigned randomly to experimental groups.

During the 15-day experimental period, the patients will be treated as follows:

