The primary outcome measure will be the incidence and rate of “relapse,” defined as a blood pressure level that has risen to the baseline value (blood pressure value of the participant at the time of enrollment) for three consecutive days.

If, over the course of 15 days there is evidence of a gradual recurrence of symptoms, the experimental period can be extended. If there is no evidence of impending relapses, there are two options: (a) we can reduce the partial reinforcement schedule from 25% to 15%, for example, and adjust the dose of in the Dose Control Groups accordingly; or (b) proceed to a study of extinction effects (Experiment 2).

Timeline estimate. We propose a start-up period of 6 mo. (formulation of Consent Form, IRB approval of protocol, preparation of study personnel, data management procedures, preparation and placing of advertisements for study subjects, etc). Including an instructional session and testing of blood pressure measurements from the monitors provided to patients, patients enrolled in the study could be engaged for as many as 50-60 days. We calculate being able to process 40 patients/year. A final 6 mo. would be devoted to data processing and manuscript preparation and, thus, a total project period of 4 years.

Experiment 2. *Effects of CS exposure on the persistence of drug effects following the withdrawal of drug and the effects of partial schedules of pharmacotherapeutic reinforcement on resistance to extinction.*

Based on the time available and the outcome of Experiment 1, we may be able to gather additional preliminary data on the extinction of conditioned pharmacotherapeutic effects, adding evidence that results obtained in Experiment 1 are, in fact, the results of conditioning. We expect that patients in Dose Control Group-II from Experiment 1 will relapse within 2-3 days of the treatment imposed during the experimental period. A large percentage of Dose Control Group-I patients are also expected to relapse under a reduced dose of active drug during the experimental period. However, we expect that a significant percentage of patients in the Partial Reinforcement Group (as well as the Standard Therapy Group) would be available for further study of extinction effects.

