The Cox proportional regression model will be used to examine the time to relapse outcome, while mixed-effects (MM) model will be used to compare differences in symptom reductions over time across the treatment groups. The MM approach employed for longitudinal data analysis provides valid inference under the missing at random assumption (MAR), provided that the parametric distribution assumptions are met. The MAR model is quite general, accommodating almost all missing data mechanism that may arise in practical studies (37,38). However, in the presence of missing data, estimates in both cases may be biased if the data fails to follow the assumed statistical distributions, even with the use of the sandwich variance estimates (39). In cases where distribution assumptions are seriously violated, for example, if discrepancies between the MM and WGEE for fixed-effects show very different results, we will use clustered bootstrap methods for inference (40).

Experiment 1

AIM 1: a) PR will be more effective than DC-1 and DC-2 in reducing relapse rates. PR will have similar effectiveness to ST in reducing relapse rates.

Survival analysis will be conducted using Cox proportional hazards model. We will include dummy variables for the four treatment groups in addition to the covariates found to significantly differentiate the groups at baseline. Appropriate linear contrasts will be constructed to compare PR vs. each of the dose control groups, if a significant group difference is found.

Note that to formally confirm the equivalence between PR and ST, we must use non-inferiority tests. However, since the acceptable margin of tolerable difference is difficult to define due to the lack of insufficient literature on this topic, we will not conduct such a formal analysis. The effect size will provide similar indications of treatment difference.

b) PR will have higher (similar) symptom reductions than DC-1 and DC-2 (ST).

Longitudinal methods will be applied to compare the outcomes of pruritus and biologic measures across the four groups as well as the appropriate pairwise comparisons. We will dummy code the treatment conditions, include time and time by treatment interaction in addition to the covariates found to differentiate

the four groups at baseline. The hypothesis will be supported if a significant time by treatment interaction is found. Appropriate linear contrasts will be performed to compare PR vs. DC-1, DC-2 and ST.

Experiment 2

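### PR vs DC-1 mixes conditioning with capsule strength and timing, and no rule makes the conditioning claim depend on DC-2

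*Combined protocol and SAP*

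**What the plan says.** All places are in the combined protocol and SAP.

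- **Hypothesis.** Section I(a), hypothesis 1, and its restatement under Experiment 1 compare a partial schedule with the same amount of drug given continuously. The restatement expects that "patients treated under a noncontinuous schedule of medication will be less likely to show a recurrence of symptoms". The comparator described is DC-1.
- **Power.** Section II(b) plans to "recruit 37 subjects for each of the ST, PR and DC1 treatment conditions, and 10 subjects for the CD2 group" and states: "The study has 93% power to detect a 50% difference in relapse rate between group 2 and group 3 over the 2-week assessment period". In the order listed, groups 2 and 3 are PR and DC-1.
- **Arms.** Under Experiment 1, PR receives the full 12.5 mg capsule on 25% of occasions, with no more than two placebos in a row. In DC-1, "each packet will contain only 25% of the active drug received during the baseline period". The 25% schedule is justified by the statement that "lower doses (particularly this much lower) are likely to have minimal if any pharmacologic effect". The next sentence draws the conclusion for the total daily 6.25 mg.
- **DC-2.** The psoriasis part of Preliminary Studies raises the possibility that the reduced amount of drug is effective by itself, and adds a second dose control for that reason. Experiment 1 repeats this purpose.
- **Outcome.** The criterion for relapse reads: "blood pressure level that has risen to the baseline value (blood pressure value of the participant at the time of enrollment) for three consecutive days".
- **Analysis.** Section III(c) names both PR vs DC-1 and PR vs DC-2 as principal. Aim 1(a) adds: "Appropriate linear contrasts will be constructed to compare PR vs. each of the dose control groups, if a significant group difference is found".

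**The concern.** Equal milligrams give equal drug effect only if response is proportional to dose at the capsule level, and the protocol does not claim this. PR patients keep taking the capsule strength that produced their qualifying response; DC-1 patients never do. A 25% schedule gives on average 1.5 full capsules in any three days (6 occasions × 0.25). Such a capsule can break the run of three consecutive days that defines relapse. PR could therefore relapse less than DC-1 for purely pharmacologic reasons. With a different dose-response it could relapse more, which would hide a real conditioning effect.

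DC-2 takes active drug without the intervening capsules, so it is the arm that can separate these explanations. Yet hypothesis 1 is worded so that PR vs DC-1 alone would support it, and that is the only relapse contrast with a power calculation. At stake is whether a positive PR vs DC-1 result would be reported as conditioning when it shows only a schedule effect.

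**Working it through.** **1. The stated 93% power.** The inputs in section II(b) are 37 per arm, 10% dropout (37 × 0.9 = 33.3) and two-sided alpha 0.05. The DC-1 relapse rate is not given, and neither is the scale of the 50% difference. Three readings:

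- Hazard ratio 0.5: at most 81% power, even if every patient relapses (Schoenfeld, 66.6 events).
- 50 percentage points: about 99%.
- 50% relative reduction, assuming 80% in DC-1 and 40% in PR: pooled SE = √(0.6 × 0.4 × 2/33.3) = 0.120; unpooled SE = √((0.16 + 0.24)/33.3) = 0.110; z = (0.40 − 1.96 × 0.120)/0.110 ≈ 1.50; power about 93%. A Lakatos-type log-rank calculation gives 92.6% at 76% vs 38%.

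The powered difference is thus most likely a halving of relapse from somewhere near 76% to 80%, but that rate is an assumption.

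**2. The milligram match over 15 days (30 occasions).**

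- DC-1: 30 × 3.125 = 93.75 mg.
- PR at 25%: 7.5 × 12.5 = 93.75 mg.
- PR with at most two consecutive placebos: each of the 10 successive triples of occasions needs at least one active capsule, so at least 10 × 12.5 = 125 mg, and 125/93.75 = 1.33. Seven or eight active capsules can cover only 7 + 2 × 8 = 23 or 8 + 2 × 9 = 26 occasions.

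The 25% schedule and the placebo limit cannot both hold.

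**3. Relapse with no conditioning.** Assumptions not in the documents: the off-drug mean equals the enrolment value; a full capsule lowers the next 12-hour reading by 10 points; daily-mean SD is 5; there is no carry-over. PR has one active capsule per block of four (strict 25%). Relapse is a daily mean at or above the enrolment value on three consecutive days. There are 20,000 simulated patients per arm.

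| Effect of a quarter-strength capsule | PR | DC-1 |
|---|---|---|
| none | 23% | 68% |
| 10% of full | 23% | 50% |
| 25% of full (linear) | 23% | 25% |
| 40% of full (concave) | 23% | 10% |

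- In the first row the relative reduction is 1 − 23/68 = 66%, and the two-proportion test with 33.3 per arm rejects about 97% of the time (z = (0.45 − 1.96 × 0.122)/0.109 ≈ 1.94).
- With SD 8, PR is about 38% and DC-1 about 68%, 57% and 40% in the first three rows.
- With 12-hour carry-over of 0.5 applied to every arm (SD 5), the linear case is still about equal: 6% in PR, 5% in DC-1.
- If PR observes the placebo limit, its relapse falls to about 12% (SD 5, no carry-over), below DC-1's 25% even under linearity.

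A second model (12 mmHg effect, SD 5 or 8, day-to-day correlation 0.3 or 0.7, half-life 4 to 10 hours, with or without a 3 mmHg upward shift) agrees in direction. At a strict 25% schedule, the relative reduction in PR vs DC-1 is 21% to 66% with a threshold response and 1% to 18% with a linear one. With a concave response PR does worse (risk ratio 1.14 to 3.1).

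**4. DC-2.** The Experiment 1 text gives DC-2 PR's active dose (12.5 mg capsules) and, in the same sentence, 6.25 mg every other day, which averages 6.25/2 = 3.125 mg/day. Table 1 gives an average of 6.25 mg/day. In the step 3 model:

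- With PR's capsule strength every other day, DC-2 relapse is about 23%, the same as PR, so PR vs DC-2 is null without conditioning.
- With 6.25 mg every other day, DC-2 relapse is about 44% (linear) to 67% (inert) against 23% in PR, so the contrast is not null.

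**5. Power for PR vs DC-2** at an assumed 40% vs 80%, with 37 and 10 patients: pooled proportion (14.8 + 8)/47 = 0.485; pooled SE 0.178; unpooled SE 0.150; z = (0.40 − 1.96 × 0.178)/0.150 ≈ 0.34; power about 63%. After 10% dropout (33.3 and 9) it is about 58%.

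**The case against.** The strongest reply is that the protocol saw this problem. It names the drug-only explanation, adds DC-2 to exclude it, makes both contrasts principal in section III(c), and words Aim 1(a) as PR being better than both dose controls. A reader might infer from the concern that the investigators overlooked the confounding; the documents do not support that. What remains is that no rule says what may be concluded when PR beats DC-1 but not DC-2, and hypothesis 1 and the relapse power statement need DC-1 alone.

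A reader might also take the low-dose sentence as the protocol's own admission that DC-1 capsules are inert while PR capsules work. It is not. The protocol applies that sentence to the total daily dose, PR's included, and carrying it down to single capsules is an inference. Section III(a) does credit one active administration in four with enough drug to prevent rebound, but that is no dose-response for blood pressure.

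The objection that the direction is not established also stands: the gap nearly vanishes under a linear response at a strict 25% schedule and reverses under a concave one.

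**Conclusion.** The concern holds as a problem of attribution. PR vs DC-1 differs in capsule strength and timing as well as in conditioning, so alone it cannot show conditioning, and a null result cannot exclude it. With no conditioning, PR can beat DC-1 by more than the halving that best explains the 93% power (23% vs 68%) if quarter strength is near inert. It can also match DC-1 or do worse. The size rests on assumed dose-response, variability and off-drug level, none of which the documents give.

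Two stronger readings are not supported. One is that PR will win without conditioning; the calculations support only that it can. The other is that PR vs DC-2 already isolates conditioning as written. That holds only if active drug exposure is the same in both arms, and the text on DC-2's dose and on PR's schedule conflicts on exactly this.

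**What to change.** 1. In hypothesis 1 and Aim 1(a) and (b), state that PR vs DC-1 alone tests a schedule effect at a nominally equal amount of drug, and that an effect is attributed to conditioning only if PR is also better than DC-2. Because both contrasts must succeed, no alpha adjustment is needed.
2. Before relying on that rule, reconcile the DC-2 descriptions in Experiment 1 and Table 1, and reconcile PR's 25% schedule with the two-placebo limit. The aim is that the documents establish whether active drug exposure is the same in PR and DC-2. No dose or schedule is proposed here.
3. Add a supporting analysis of the twice-daily readings, linked to the pharmacy's capsule sequence, that compares PR and DC-2 at the same time since the last active capsule. It uses data already collected; its power has not been worked out.

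The cost in text is small, but the conditioning claim becomes harder to reach: DC-2 has 10 patients, and power for PR vs DC-2 is about 58% to 63% at the assumed 40% vs 80%. If PR beats only DC-1, the conclusion is limited to a schedule effect.
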